### 5.3 LIFESTYLE CONSIDERATIONS

During this study, participants are asked to:

- discontinue any OTC supplements containing the active ingredients of study treatment beginning the first day of randomization and during the entire follow-up period
- record daily usage of OTC cough and cold preparations with product(s) names and daily doses taken using a 'sick' diary (not required but will be encouraged)

### 5.4 SCREEN FAILURES

Screen failures are defined as participants who consent to participate in the clinical trial but are not subsequently randomly assigned to the study intervention or entered in the study. A minimal set of screen failure information is required to ensure transparent reporting of screen failure participants, to meet the Consolidated Standards of Reporting Trials (CONSORT) publishing requirements and to respond to queries from regulatory authorities. Minimal information includes demography, screen failure details, eligibility criteria, and any serious adverse event (SAE).

Individuals who do not meet the criteria for participation in this trial (screen failure) because of a positive influenza test with intention to be treated with oseltamivir or baloxavir may be rescreened. Rescreened participants should be assigned the same participant number as for the initial screening.

### 5.5 STRATEGIES FOR RECRUITMENT AND RETENTION

Patients will be recruited through the emergency department at MUHC during study months of May 2022 – June 2023. Patients seeking routine care for respiratory viral illness related symptoms will be screened by ED medical staff for eligibility and if appropriate will be consented by key study personnel members for enrollment. The target number of subjects to be enrolled during the study period occurring May 2022 – June 2023 is 100 (50 patients randomized to placebo and 50 to the supplementation group). This target is derived from similarly conducted studies evaluating zinc supplementation (without green tea) in a comparable adult population as identified with the current proposal. The anticipated accrual rate is approximately 5-10 patients each week based on current MUHC ED patient visit volumes and prevalence of cold and flu-like illness during the study time period. MUHC is considered a safety net hospital and therefore treat patients regardless of their insurance status. This designation will allow underrepresented populations equal opportunity to participate in this study. Advertisements will be used including a flyer containing the University of Missouri School of Medicine logo that will be placed in select clinic spaces, and an email announcement distributed through the study site's email system to help increase awareness of study opportunity for interested patients or their caregivers.

## 6 STUDY INTERVENTION

### 6.1 STUDY INTERVENTION(S) ADMINISTRATION

#### 6.1.1 STUDY INTERVENTION DESCRIPTION

The compounded supplementation study product includes select amounts of zinc citrate, green tea extract, and ascorbic acid that have been mixed together using geometric dilution to form a light brown fine powder, and is capsulated using a capsule machine with size 0 empty gelatin capsules resulting in a measured weight of  $438\text{mg} \pm 10\%$  per capsule. The per capsule amount of each supplement component is as follows:

267mg of green tea extract/capsule  
104mg of zinc citrate (33mg elemental zinc)/capsule  
67mg ascorbic acid/capsule

The finished goods specification sheets, safety data sheets, and certificate of analysis (CoA) for each respective supplement has been provided by the supplier and have been attached as addendums.

Addendum A – zinc citrate specification sheet, safety data sheet, and CoA  
Addendum B – green tea extract ( $\geq 50\%$  EGCG) specification sheet, safety data sheet, and CoA  
Addendum C – ascorbic acid specification sheet, safety data sheet, and CoA

Zinc citrate is a white crystalline powder containing 32% zinc by weight. Zinc is a naturally occurring element that is essential for human health, and various salts are available over-the-counter (OTC) for supplementation purposes. The FDA approved zinc product is zinc sulfate for injection.

Green tea extract is a brown powder-like substance derived from the stems and leaves of *Camellia sinensis* through an extraction process using water and organic solvents such as ethanol. A variety of green tea extracts are available over-the-counter for supplementation and contain little to no caffeine. Extract products contain high amounts of antioxidant catechin compounds the most abundant of which is epigallocatechin-3-gallate (EGCG). The EGCG content of most available green tea extract products is 50% by weight, but variability exists due to inconsistencies in manufacturing processes. The FDA approved a green tea extract product in 2006 called Veregen® (sinecatechins) ointment, which was the first prescription botanical accepted by the governing body.

Ascorbic Acid commonly known as vitamin C is available as a white crystalline powder and available over-the counter for oral supplementation. It is an essential nutrient naturally found in food sources and is FDA approved for the treatment of scurvy.

Placebo capsules will be filled with microcrystalline cellulose, which is refined wood pulp commonly used in food production as an anti-caking or bulking agent. It is a chemically inert compound with no appreciable absorption following oral administration, and has been rarely reported to induce an allergic reaction. The per capsule amount of microcrystalline cellulose is as follows:

300mg ± 10% of microcrystalline cellulose/capsule

The certificate of analysis for microcrystalline cellulose is attached as an addendum.

Addendum D - microcrystalline cellulose CoA

#### 6.1.2 DOSING AND ADMINISTRATION

Eligible patients will be randomized 1:1 to one of the following treatment groups with the following dosing schedule:

1. Zinc/EGCG/ascorbic acid blend: three (3) capsules taken orally two (2) hours following a meal twice daily x5 days.
2. Placebo: three (3) capsules taken orally two (2) hours following a meal twice daily x5 days

The per capsule and total daily dose of each of the individual supplement components is as follows:

267mg green tea extract/capsule (1,600 mg/day)  
33mg elemental zinc/capsule (200 mg/day)  
67mg ascorbic acid/capsule (400 mg/day)

The per capsule and total daily dose of each of the placebo component is as follows:

300mg microcrystalline cellulose/capsule (1,800 mg/day)

Patients will be instructed to begin taking their assigned study product starting the evening of enrollment day and to continue for five consecutive days. For missed doses study participants will be instructed not to double up on doses and to take the prescribed dose at the next scheduled administration time. Study product should be stored away from children so to avoid unintended administration by unauthorized study participants.

Study participants who will be undergoing blood sampling procedures will not be randomized or receive placebo.

#### 6.2 PREPARATION/HANDLING/STORAGE/ACCOUNTABILITY

##### 6.2.1 ACQUISITION AND ACCOUNTABILITY

Active ingredients for the zinc/EGCG/ascorbic acid blend will be procured from a U.S. based supplements supplier ([www.bulksupplements.com](http://www.bulksupplements.com); FDA registration number: 17938017996) at the following amounts factoring in a 20% waste tolerance and available package size.

1. Zinc citrate – 200g
2. Green tea extract (≥50% EGCG) – 500g
3. Ascorbic acid – 200g

Placebo ingredients will be procured from the MUHC investigation pharmacy services at the following amounts factoring in a 20% waste tolerance and available package size.

### 1. Microcrystalline cellulose – 1kg

Compounded capsules of both the study supplement product and placebo will be assessed for weight variability with a 10% variance allowed. Capsules will be prepared in small batches throughout the study period based on the anticipated weekly accrual rate of enrollment. Each batch will be assigned a unique lot number, their own compound log, and up to a 180 day expiration date. Storage will occur in the investigational drug pharmacy where compounded capsules will be kept in a standard amber colored prescription bottle with a desiccant placed within the bottle to absorb any ambient moisture.

Temperature monitoring will occur daily by the investigation drug pharmacist with a target range of 20°C – 25°C per United States Pharmacopoeia (USP) and the supplement manufacture's recommendations. The investigational drug pharmacist or designated pharmacist will receive a study prescription from an authorized prescriber following patient enrollment for processing, which includes assignment of randomization, filling of prescription with required documentation and labeling, and coordination with the ED study staff for delivery to the patient in the ED. Study patients will be discharged from the ED with their study drug before returning home later that day. Unused study drug returned by participants will be received by the investigational drug pharmacy for proper documentation, storage, and eventual destruction.

---

#### 6.2.2 FORMULATION, APPEARANCE, PACKAGING, AND LABELING

Study products will be prepared using University of Missouri Health Care (MUHC) pharmacy compounding resources using traditional practices of geometric dilution and capsulation. Compounding and dispensing of study supplement and placebo will be in compliance with Missouri Board of Pharmacy regulation 20 CSR 2220.2.400 Compounding Standards of Practice. White, opaque size 0 gelatin capsules will be used to prepare both study supplement and placebo, and will be dispensed into amber prescription bottles with tamper resistant tops for patient delivery. Labeling of study product will be in such a way to maintain blinding, but will include all information as required by state and federal regulations including: 1) The date the prescription was filled; 2) A prescription number or other unique identifier; 3) The patient's name; 4) The prescriber's directions for use; 5) The prescriber's name; 6) The pharmacy/institution's name, address, and contact information; 7) blinded name of study drug dispensed. The Federal Investigational Drug Caution Statement—"CAUTION: Drug limited by Federal (United States) Law to investigational use only."—will be applied to the study drug products.

---

#### 6.2.3 PRODUCT STORAGE AND STABILITY

Storage requirements for study products will be in accordance with the individual component manufacture recommendations and USP. This includes keeping compounded capsules in a dry and cool environment with a target temperature of 20°C – 25°C. To minimize moisture a desiccant will be placed in the bulk bottles containing prepared study supplement and placebo capsules, respectively. An expiration date of up to 180 days will be given to compounded capsules to limit any unknown loss of potency that may occur with a long-dated expiration. This dating is in accordance with United States Pharmacopeia (USP) General Chapter 795 guidance for non-sterile compounding.

---

#### 6.2.4 PREPARATION

Study capsules for combination supplementation will be prepared by compounding each of the three individual components using a porcelain mortar and pestle and method of geometric dilution. The mixed fine powder will be used to fill white colored size 0 gelatin capsules using a capsule machine with a 100 capsule capacity. A 10% variability tolerance will be permitted for under/over filling of each capsule with a target weight of 438mg per capsule. Placebo capsules will be prepared in a similar fashion using microcrystalline cellulose with identical capsules and a fill weight target of 300mg ± 10%. All compounding will occur on site at MUHC in a dedicated non-sterile compounding room located in the inpatient pharmacy.

### 6.3 MEASURES TO MINIMIZE BIAS: RANDOMIZATION AND BLINDING

Randomization will be performed using an online generator (<http://www.randomization.com>) that assigns study subjects to a single treatment arm using randomly permuted blocks. The investigational drug pharmacist will conduct maintenance of trial randomization codes and appropriate blinding. Double blinding will be used to limit recall and observer bias given the subjectivity of the primary outcome. Opaque, white colored capsules of the same size will be used to prepare both study supplement and placebo capsules to conceal treatment assignment. Serious adverse events requiring medical care that are suspected to be caused from the study drug or an unintentional ingestion of study drug by non-study participants will initiate un-blinding procedures. This will include contacting research pharmacy personnel or their designee by medical staff treating the adverse event. Research pharmacy personnel are available during normal business hours, however, their designee (other MUHC inpatient pharmacists) will be available 24 hours a day, seven days a week. Treating medical staff will be immediately informed of the study subject's randomization assignment by the research pharmacist or their designee for purposes of emergent medical care; recording of the unblinding will be performed by the research pharmacist and notification will be sent to the primary investigator and Independent Safety Monitor within 24 hours. Documentation of an unblinding event will include: identification of participant unblinded, reason for unblinding, date and time of unblinding, how unblinding information was obtained, and which research team member(s) have been unblinded. Study participants will be removed from the study if they experience an adverse event that requires medical care due to complications from worsening respiratory viral illness or study drug. Patients not removed will be contacted daily via telephone visits for seven consecutive days by MUHC emergency department research staff starting the day after enrollment day for collection of primary and secondary outcome data elements. MUHC emergency department research staff are trained technicians autonomous of study teams for purposes of clinical trial and facilitate independent data collection for study endpoints. Following the seven days of follow-up patients will be dismissed from study participation and will be instructed to follow-up with their primary care provider for any future medical needs.

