### 7 STUDY INTERVENTION DISCONTINUATION AND PARTICIPANT DISCONTINUATION/WITHDRAWAL

#### 7.1 DISCONTINUATION OF STUDY INTERVENTION

Discontinuation from study supplement or placebo does not mean discontinuation from the study, and remaining study procedures should be completed as indicated by the study protocol. If a clinically significant finding is identified (including, but not limited to changes from baseline) after enrollment, the investigator or qualified designee will determine if any change in participant management is needed. Any new clinically relevant finding will be reported as an adverse event (AE).

Adverse events necessitating discontinuation from the study including removing patients from follow-up telephone visits for any remaining outcome related data collection include any event that would lead to a patient requiring hospitalization. This includes hospitalization related to a suspected adverse event from study drug resulting in unblinding procedures or for worsening respiratory status. Patient self-discontinuation of study intervention due to intolerance affecting future compliance will allow patients to remain in the study to complete any remaining telephone visits for primary and secondary endpoint data collection. Efforts to promote compliance including reinforcing patients to administer study product two hours following a meal will be employed before discontinuing patients from study intervention, but patient refusal to continue with treatment will be considered a dropout with an attempt to collect remaining telephone visits for completeness of endpoint related data capture.

The data to be collected at the time of study intervention discontinuation will include the following:

- Date of study discontinuation
- Reason for discontinuation
- Number of study days completed prior to discontinuation of treatment/study withdrawal
- Total number of patient-reported doses taken of study drug prior to discontinuation of treatment/study withdrawal

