## 7.2 PARTICIPANT DISCONTINUATION/WITHDRAWAL FROM THE STUDY

Participants are free to withdraw from participation in the study at any time upon request.

An investigator may discontinue or withdraw a participant from the study for the following reasons:

- Pregnancy
- Significant study intervention non-compliance
- If any clinical adverse event (AE) necessitating hospitalization
- Disease progression which requires hospitalization
- If the participant meets an exclusion criterion (either newly developed or not previously recognized) that precludes further study participation

The reason for participant discontinuation or withdrawal from the study will be recorded. Subjects who sign the informed consent form and are randomized but do not receive the study intervention may be replaced. Subjects who sign the informed consent form, and are randomized and receive the study intervention, and subsequently withdraw, or are withdrawn or discontinued from the study may also be replaced.

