#### 9.4.2 ANALYSIS OF THE PRIMARY EFFICACY ENDPOINT(S)

The primary endpoint will be determined from observing the proportion of patients (expressed as percentage) recovered from cold and flu-like symptoms (defined as scoring 0 or 1 daily total symptom severity score) following seven days of follow-up. Recovery from cold and flu-like symptoms will be categorically assessed as a single endpoint. The difference in recovery rates between study drug and placebo will be compared using Chi-squared test and be expressed with 95% confidence intervals. Analysis will be performed based on intention-to-treat. Missing data will be handled by last observation carried forward based on most recent self-reported total daily symptom severity score.

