#### 9.4.3 ANALYSIS OF THE SECONDARY ENDPOINT(S)

Secondary endpoints are independent of findings from the primary endpoint.

Rates of adverse events will be determined as a percentage of those subjects self-reporting an event compared to the total cohort following seven days of follow-up. Adverse events will be categorically expressed as a single endpoint. Difference in adverse events will be compared using Chi-squared test with incidence rates expressed as percentages. Analysis will be performed based on intention-to-treat. Missing data will be handled by last observation carried forward based on most recent self-reported adverse event (or lack thereof).

Rates of missed days of work or school will be determined as a percentage of those subjects self-reporting a missed day compared to the total cohort following seven days of follow-up. Missed days will be both categorically expressed as a single endpoint with incidence rates expressed as percentages as well as mean days missed with standard deviation. Difference in missed days will be compared using Chi-squared test for categorically expressed missed days (occurrence of any missed day(s) during study follow-up) and student's t-test for mean days missed. Analysis will be performed based on intention-to-treat. Missing data will be handled by last observation carried forward based on most recent self-reported missed day (or lack thereof).

Rates of seeking medical care including physician office visits or hospitalization for worsening respiratory illness will be determined as a percentage of those subjects self-reporting these events compared to the total cohort following seven days of follow-up. A physician office visit or hospitalization for worsening respiratory illness will be categorically expressed as a single endpoint with incidence rates expressed as percentages. Difference in need to seek medical care will be compared using Chi-squared tests. Analysis will be performed based on intention-to-treat. Missing data will be handled by last observation carried forward based on most recent self-reported medical visit (or lack thereof).

---

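### Section 6.3 ends study participation after any adverse event needing medical care, while 7.1 and 7.2 set the threshold at hospitalization; followed as written, 6.3 cuts the primary outcome short

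*Combined protocol and SAP*

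**What the plan says.** **Section 6.3 (randomization and blinding).** "Study participants will be removed from the study if they experience an adverse event that requires medical care", provided the event stems from complications of the respiratory illness or from study drug. The next sentence ties outcome collection to this: "Patients not removed will be contacted daily via telephone visits for seven consecutive days". Removal is mandatory, and no level of seriousness is given.

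**Section 7.1 (discontinuation of study intervention).** Stopping product is not leaving the study. Adverse events that end participation and the calls "include any event that would lead to a patient requiring hospitalization". For those who cannot tolerate the product: "Patient self-discontinuation of study intervention due to intolerance affecting future compliance will allow patients to remain in the study". For those who refuse further treatment, the remaining calls are still attempted.

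**Section 7.2 (withdrawal from the study).** "An investigator may discontinue or withdraw a participant from the study for the following reasons"; the adverse-event and disease-progression reasons listed there are both tied to hospitalization.

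**What counts as medical care.** The secondary safety endpoint in the synopsis (1.1) and in section 3 gives hospitalization or a physician visit as examples. Section 9.4.3 has "Rates of seeking medical care including physician office visits or hospitalization for worsening respiratory illness" as a secondary endpoint.

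**Analysis.** Section 9.3 analyses all randomized participants. For the primary endpoint, 9.4.2 says: "Missing data will be handled by last observation carried forward based on most recent self-reported total daily symptom severity score". Recovery is a daily total of 0 or 1 out of 36.

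**The concern.** The two thresholds give different primary data for the same person. Someone who sees a physician, is not admitted, and is still symptomatic leaves the study under 6.3 but is not named for removal under 7.1 or 7.2. In the first case the outcome is imputed; in the second it is observed to Day 8. Because recovery requires a score of 0 or 1, carrying forward an early score above 1 fixes the result as not recovered.

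The event that stops collection is itself a secondary endpoint (a visit for respiratory complications) or a safety endpoint (a visit for a suspected drug effect). It is therefore related to how the participant is doing and may differ by arm: section 2.3.3 expects additive nausea on the combination. Keeping everyone in an intention-to-treat set does not help if the value entered for some of them depends on which section staff applied.

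**Working it through.** **1. The rules side by side, for a physician visit on Day 3, no admission, score above 1**

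| | Section 6.3 | Sections 7.1 and 7.2 |
|---|---|---|
| Threshold | Medical care for illness or drug complications | Hospitalization |
| This participant | Removed | Not named for removal |
| Calls after Day 3 | None | Days 4 to 8 |
| Primary outcome | Day 3 score carried forward: not recovered | Observed |

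Calls run from Day 2 to Day 8, which is 7. After the Day 3 call, 5 of the 7 are lost.

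**2. The plan's own sample size (section 9.2)**

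Inputs: 60% vs 30% recovery, two-sided 0.05, 80% power, 1:1 allocation.

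N per arm = (1.96 × √(0.45 × 0.55 × 2) + 0.84 × √(0.30 × 0.70 + 0.60 × 0.40))² / 0.30² = 41.9, rounded up to 42, so 84 in total. The stated figure reproduces. Allowing for 5% dropout, 84 / 0.95 = 88.4, so 89, which is below the target of 100.

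**3. Effect of removal, with 50 per arm**

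The documents give no rate of physician visits, so the numbers removed, r, are assumptions. All are taken to be removed with a last score above 1.

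- Under 6.3, recoveries in an arm follow Binomial(50 − r, p), and the r removed count as not recovered.
- If followed, recoveries follow Binomial(50 − r, p) plus Binomial(r, f × p). Here f is the fraction of the planned rate at which these people would recover.
- p is 0.60 on active and 0.30 on placebo.
- Power is the exact probability that the uncorrected chi-square exceeds 3.84.

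With nobody removed, the difference is 30 points and power is 0.876.

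Worked example, 5 vs 2 removed: active 0.60 × 45/50 = 54.0%; placebo 0.30 × 48/50 = 28.8%; difference 25.2 points. If followed at f = 0.5: active 54.0% + 0.30 × 5/50 = 57.0%; placebo 28.8% + 0.15 × 2/50 = 29.4%; difference 27.6 points.

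| Removed (active vs placebo) | Under 6.3 | Followed, f = 0.5 | Followed, f = 1 |
|---|---|---|---|
| 3 vs 2 | 27.6 points, power 0.825 | 28.8 points, 0.851 | 30.0 points, 0.876 |
| 5 vs 2 | 25.2 points, 0.753 | 27.6 points, 0.820 | 30.0 points, 0.876 |
| 5 vs 10 | 30.0 points, 0.895 | 30.0 points, 0.882 | 30.0 points, 0.876 |

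The choice of f matters. For 5 vs 2, f = 0.25 gives power 0.79 if followed. At f = 0 the two rules give the same result and nothing is lost.

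**The case against.** **The sections can be reconciled.** The 6.3 sentence follows text on unblinding for serious events, and the two sections devoted to discontinuation both use hospitalization. A coordinator might sensibly read 6.3 that way. This is possible, but the text does not say it: the removal sentence does not limit itself to serious events, and the plan uses medical care to cover physician visits. Section 7.1 says its events *include* hospitalization, so its list may not be exhaustive. That softens the contradiction, but it leaves 6.3 in force and ends calls after an office visit.

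**The size is assumed.** This stands. So does the point that people seeking care for worsening illness may not reach a score of 0 or 1 by Day 8; a lower bound of half the planned rate has no support in the documents. The imbalance expected from nausea would also shrink an apparent benefit, not create one.

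**Stronger readings that the documents do not support**

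- *7.2 contradicts 7.1.* A reader might set the optional withdrawal in 7.2 against the necessary one in 7.1, or take "Significant study intervention non-compliance" to catch the intolerance stoppers. A list of permitted reasons can coexist with 7.1, which deals with those participants expressly and keeps them in.
- *The plan expects this loss.* The 5% dropout in 9.2 comes from a 12-month EGCG study and is general dropout. It is not a rate of removal for medical care.
- *The trial is underpowered.* The sample size reproduces, and the target exceeds it.
- *The 9.4.4 discontinuation listing cannot be produced.* Sections 7.1 and 8.1 already collect date, reason, days completed and doses taken.

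**Conclusion.** The inconsistency is real and lies between 6.3 and the hospitalization threshold in 7.1 and 7.2. Followed literally, 6.3 stops primary data collection because of a secondary or safety event and turns a still-symptomatic score into a final non-recovery. The plan should resolve this, but it is not a demonstrated failure of the primary analysis.

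Under assumed removals of 3 vs 2, power is 82%, against 85% to 88% with follow-up. Under 5 vs 2 it is 75%, against 82% to 88%. These ranges assume the planned 60% vs 30%, that everyone removed is symptomatic at their last call, and that they would otherwise recover at half to all of the planned rate. Only participants who would have recovered later change the result. The loss is zero if none would have, and negligible if removals are more frequent on placebo.

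**What to change.** Replace the removal sentence in 6.3 with: *Participants who stop study product or need medical care for an adverse event remain in the study and are called through Day 8 unless they withdraw consent.* Align 7.1 and 7.2 with it. This extends to medical care the principle 7.1 already applies to stopping product.

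If hospitalized participants must leave the calls, say so in identical words in 6.3, 7.1 and 7.2, count them as not recovered, and report the number in each arm.

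The cost is a protocol amendment with IRB approval and, for each affected participant, a few extra calls. Some calls to people who are unwell will go unanswered, so some carry-forward will remain. Alpha and sample size are unaffected.
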